9.4.2 Secondary Analyses

The 95% confidence intervals will be computed for the sloughing rates for each treatment group using the Wilson score method. Significant trends in incidence rates across the treatment groups (from high to medium to no SLS toothpaste) will be tested using the Cochran Armitage test.

The oral mucosal sloughing index score will be used to compute the following two outcomes: (a) Overall subject-level incidence based on any non-zero score among the 12 oral areas examined, and (b) an average subject-level score based on the mean of 12 severity scores over all oral areas for each subject. These outcome scores will be summarized for each treatment group and if appropriate, will be analyzed using a generalized linear regression model such as a Poisson model to test for significant treatment, period and sequence effects.

The diary data will be used to compute treatment compliance with expected number of doses, and this will be summarized per period and treatment group.

Exploratory analysis may occur to examine the onset time and duration of adverse events.

The data collected on the subject acceptance questionnaire will be summarized by treatment group. If appropriate, these data will be analyzed for treatment differences using a generalized linear regression model such as an ordinal logistical model that takes into account the cross over design and the ordinal nature of the data.

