8.0 Randomization

8.1 Randomization

Subjects will be numbered from 01 through 72. This number will be used to identify the subject on the case report forms. Subjects will be randomized in a 1:1:1 ratio into three different two-treatment sequences: (1) A-> C (2) B->C and (3) C->B. All seventy-two (72) subjects will be exposed to the high SLS toothpaste (C), 48 subjects will be exposed to the medium SLS toothpaste (B), and 24 subjects will be exposed to the no SLS toothpaste (A). See Appendix II for the randomization schedule.

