9.0 Data Analysis

9.1 Statistical Hypothesis

[figure not shown]
The main hypothesis under investigation is that the incidence of sloughing over a 3-week period will be positively correlated with the level of SLS in the toothpaste assigned.

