9.2 Sample Size Determination

A sample size of 72 represents a convenient sample size that should yield incidence rate estimates of adequate precisions to detect gross trends.

A sample size of 24 will give a precision (1/2 confidence interval width) of 4% if the observed incidence rate is 1%. Likewise, sample size of 48 will give precisions of 8.5-13% for incidence rates 10-30%, and a sample size of 72 will give precisions of 11.3-11.5% of incidence rates of 40-50%.

In addition, sample sizes of 72 and 48 will give 74% power to detect differences in proportions of 50% and 25%, respectively. Furthermore, sample sizes of 48 and 24 will give 77% power to detect differences in 25% and 1%, respectively using a two-sided Fisher's exact test with alpha of 0.05.

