9.3 Populations for Analysis

The datasets that will be used for the primary and secondary analyses including the adverse event analysis will include all subjects randomized into the study (intent-to-treat population). There will be no additional subset datasets defined for other analyses or sensitivity analyses.

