9.4.1 Primary Analyses

The primary endpoint is the incidence rate of sloughing. All sloughing clinically observed or subject-reported over the three-week treatment period will be recorded as an adverse event and coded using the MedDRA dictionary (with a preferred term of oral mucosal exfoliation). Differences in incidence rates will be tested for significance using a generalized logistic regression model that takes into account the crossover design with subject as a random effect and treatment, period, sequence and treatment-by-period interaction as fixed effects, non-significant treatment-by-period interaction effect will be dropped from the final model. In the event of failing convergence of the model or finding a significant treatment-by-period interaction (carry-over effect), the Fisher's Exact test maybe used to test for significant differences in sloughing rates among the treatment arms using all data or Period I data only, respectively.

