9.6 Procedures for Missing, Unused, or Spurious Data

Missing data due to subject withdrawals or subjects lost to follow-up will not be imputed. All data collected from each subject will be used in the statistical analyses.

[figure not shown]

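### The only ordered test of the SLS hypothesis, a secondary Cochran-Armitage test, ignores subject and period although the no-SLS toothpaste is used only in Period 1

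*Combined protocol and SAP*

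**What the plan says.** Section 9.1 states an ordered hypothesis: "the incidence of sloughing over a 3-week period will be positively correlated with the level of SLS in the toothpaste assigned".

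The primary model in 9.4.1 has "subject as a random effect and treatment, period, sequence and treatment-by-period interaction as fixed effects". It tests differences in incidence between treatments and states no SLS score or trend contrast. Its fallback, and the adverse event comparison in 9.4.3, are Fisher's exact tests, which are also unordered.

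The only test of order is in 9.4.2, where trends across the groups "from high to medium to no SLS toothpaste) will be tested using the Cochran Armitage test". No subject or period term is given, and the records to be used are not stated. The same section does adjust elsewhere: the sloughing index model is to "test for significant treatment, period and sequence effects", and the questionnaire model is to allow for the crossover.

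Three statements bear on which records enter:

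- 9.3: "There will be no additional subset datasets defined for other analyses or sensitivity analyses".
- 9.6: "All data collected from each subject will be used in the statistical analyses".
- 9.2: "sample sizes of 72 and 48 will give 74% power to detect differences in proportions of 50% and 25%, respectively", followed by a comparison of 48 with 24.

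Section 8.1 gives the sequences A-C, B-C and C-B in a 1:1:1 ratio. All 72 subjects receive toothpaste C, and "48 subjects will be exposed to the medium SLS toothpaste (B), and 24 subjects will be exposed to the no SLS toothpaste (A"). Toothpaste A is therefore a study treatment only in Period 1.

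**The concern.** Cochran-Armitage is a test for independent binomial groups. Applied to all exposures, it treats two records from one subject as if they came from two people, and it compares groups with different mixes of periods. That mix follows the SLS order, so the period effect and the SLS trend are confounded in the pooled table.

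The result could be wrong in either direction. If sloughing is more frequent in Period 2, an SLS trend appears where there is none; if it is less frequent, a real trend is diluted. A period effect is plausible because every Period 2 record follows a first three-week course of the same rinse (3.1), and 9.4.1 itself fits period. The affected test is the only one that addresses the stated hypothesis in its ordered form.

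**Working it through.** **The plan's own figures.** Section 9.2 gives no power or error rate for the trend test. Its Fisher powers of 74% (72 v 48 at 50% v 25%) and 77% (48 v 24 at 25% v 1%) reproduce as 74.2% and 77.6%, with the two-sided p-value taken as twice the one-sided. So 9.2 does plan on 72, 48 and 24 exposures as groups.

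**Period mix (24 subjects per sequence, 8.1 and Appendix II).** Share of records in Period 2: A 0/24 = 0%; B 24/48 = 50%; C 48/72 = 67%.

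**The statistic.** With scores 0, 1, 2 and n = 24, 48, 72:

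- Mean score = (48 + 144)/144 = 4/3, so the centred scores are A −4/3, B −1/3, C +2/3.
- Sum of squares = (48 + 288) − 192²/144 = 80, so the test uses variance 80·p(1−p), where p is the pooled rate.

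*Pairing.* Within-subject products of centred scores are −8/9 (A-C), −2/9 (B-C) and −2/9 (C-B). For within-subject correlation ρ the true variance with equal rates is p(1−p)·[80 + 2·24·(−12/9)·ρ] = p(1−p)·(80 − 64ρ). It is below the assumed variance whenever ρ > 0, so ignoring the pairing alone makes the test conservative.

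*Period.* With no SLS effect and a shift of δ from Period 1 to Period 2, the numerator has expectation 24·(2/3 + 2/3 − 1/3)·δ = 24δ. It should be zero.

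| Period 1 to Period 2 | Expected A / B / C | 24δ | √(80·p(1−p)) | z |
|---|---|---|---|---|
| 20% to 30% | 20 / 25 / 26.7% | 2.4 | √(80·0.25·0.75) = 3.87 | 0.62 |
| 20% to 40% | 20 / 30 / 33.3% | 4.8 | √(80·0.30·0.70) = 4.10 | 1.17 |
| 40% to 20% | 40 / 30 / 26.7% | −4.8 | 4.10 | −1.17 |

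For z = 1.17 and independent records the normal approximation gives a rejection rate of about 22%, close to the upper end of the simulated range below.

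**Simulated rejection with no SLS effect** (random-intercept logistic data, 20,000 trials per case, nominal 5%; SD is the assumed subject SD):

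| Period effect | SD 1.5 | Range, SD 0 to 3 |
|---|---|---|
| 20% in both periods | 3.0% | 1.2–4.8% |
| 20% to 30% | 6.2% | 3.4–9.0% |
| 20% to 40% | 17.9% | 14.2–20.4% |
| 40% to 20% | 20.1% | 17.4–22.0% |
| Within-subject OR 2 from 20% | 5.6% | 1.9–12.1% |
| Within-subject OR 3 from 20% | 11.9% | 3.5–25.4% |

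In the 40% to 20% case almost all rejections are opposite to the hypothesis. Cochran-Armitage on Period 1 alone stays at 4.7–5.7% throughout. A linear SLS term with period and a random subject intercept (likelihood-ratio test, 2,000 trials per case) gives 4.5–6.5% over nine null cases.

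**Power at assumed rates for no/medium/high SLS** (SD 1.5):

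| Case | Cochran-Armitage, all exposures | Linear SLS term with period |
|---|---|---|
| 10/20/30%, no period effect | 60% | 60% |
| 10/20/30%, Period 2 OR 0.5 | 34% | 58% |
| 15/25/40%, no period effect | 76% | 77% |
| 15/25/40%, Period 2 OR 0.5 | 50% | 74% |
| 1/25/50% (9.2), either | at least 99.6% | at least 99.6% |

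**The case against.** **The records are not stated.** If Period 1 alone was meant, the objection largely falls away. Section 9.3 defines which subjects are analysed, 9.6 concerns missing data, and 9.4.1 already allows a Period 1 analysis as a fallback. This stands in part: the all-exposures reading is an inference. It remains the natural one, because 9.2 and 8.1 work with groups of 72, 48 and 24, and 9.4.1 names Period 1 explicitly where it means it. If Period 1 was intended, 9.4.2 has to say so.

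**The primary analysis is protected.** It adjusts for subject and period, and its estimates would show the order. This is true and limits the weight of the point. But its test is not of order, and the pooled trend p-value would still be reported as the test of the ordered hypothesis.

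**The harm is assumed.** No period effect is given. There is a rinse-free washout of at least one week, and section 5.2 expects effects to be transient. The larger inflation needs the rate to double or halve between periods. For a 10-point shift at SD 1.5 the two tests reject equally often (6.2% each), and with no period effect Cochran-Armitage is the more conservative (3.0% v 5.8%). All of this stands as a limit on size. The direction of the bias, however, follows from the sequences alone.

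**At the planning rates nothing changes.** Correct. But 9.2 calls the sample size a convenient one, so those rates do not guarantee a steep effect.

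**Conclusion.** The concern holds. The hypothesis is ordered, and its only ordered test omits the period term that this design needs, because the no-SLS treatment never occurs in Period 2. Omitting period does the harm; ignoring the pairing alone errs on the safe side.

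The size depends on assumptions the documents do not settle: that all exposures enter the test, how large the period effect is, whether it is defined on marginal rates or within subject, and the subject SD. Under a 20-point marginal shift, false rejection is roughly 14–22%. Under a 10-point shift or an odds ratio of 2 it is slight at SD 1.5, and at odds ratio 2 with SD 2 it is absent (3.8%). A Period 2 odds ratio of 0.5 costs about 24 to 26 points of power at moderate SLS effects and nothing that matters at 1/25/50%. This should be fixed, but it does not undermine the primary analysis. Confidence is medium.

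**What to change.** Replace the Cochran-Armitage sentence in 9.4.2 with text such as:

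> The 9.1 trend across SLS levels will be tested, two-sided at 0.05, by a 1-df likelihood-ratio test of SLS level as a linear term (no = 0, medium = 1, high = 2) in a logistic model with a random subject intercept and period, using both periods. Adding sequence is a sensitivity analysis. A Cochran-Armitage test on Period 1 only (24/24/24 independent subjects) is supportive, and replaces the model if it does not converge.

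Keep the 9.4.1 treatment test as it stands. Note the Period 1 use in 9.3 for consistency; 9.4.1 already relies on such an analysis, so this only tidies the text. If Cochran-Armitage on all exposures is kept, label it descriptive.

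The cost is wording and a few lines of code. If outcome data have been seen, report the change as a deviation under 9.7. The downsides are:

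- The likelihood-ratio test runs slightly above 5% (4.5–6.5%; 5.2–7.1% with sequence). For period shifts up to 10 points at SD 1.5 it has no size advantage.
- Equal spacing is a choice, since the documents give only no, medium and high.
- A linear term can miss a non-monotone response: 3% power against 50% for the 2-df treatment test (with sequence) at an assumed 10/35/20%. That is why the 9.4.1 test is kept.
- With no period effect, Period 1 alone has less power than Cochran-Armitage on all exposures: 41% v 60% at 10/20/30%, and 51% v 76% at 15/25/40%.
- Adding sequence costs about 2 to 5 points of power: 57% v 60% and 75% v 77% without a period effect, 53% v 58% and 71% v 74% with Period 2 OR 0.5.

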9.4.3 Adverse Event Analyses

Adverse event data will be coded using the MedDRA dictionary and the incidence rates will be summarized by preferred term and treatment group. Differences in incidence rates among the three groups will be tested using an overall Fisher's exact test and further pairwise testing (A vs B, A vs C and B vs C) will be carried out if the overall p-value is significant (<0.05).

9.5 Planned Interim Analysis

There will be no interim analyses for this study.

9.6 Procedures for Missing, Unused, or Spurious Data

Missing data due to subject withdrawals or subjects lost to follow-up will not be imputed. All data collected from each subject will be used in the statistical analyses.

[figure not shown]
9.7 Procedures for Reporting Deviations from Statistical Analysis Plan

Any deviations from the statistical analyses outlined in this protocol will be described and justified in the final study report.

10.0 Personnel Responsibilities

10.1 All Study Staff

Investigator, dental examiners, and staff are required to be current in their [REDACTED] required CITI training and to comply as stated in [REDACTED] (Preclinical and Clinical Study Overview), [REDACTED] ([REDACTED] Clinical Studies), [REDACTED] (Biocompatibility Assessment and Testing), and [REDACTED] (Preclinical and Clinical Documentation Requirements).

The Investigator or staff, including the Study Coordinator(s), will review all data entries for completeness and correctness, and then sign each individual form. All completed CRFs and copies of subject sign consent forms are to be retained. When changes or corrects are made on any form, study staff must draw a single line through the error, initial, and date.

10.2 Principal Investigator

The Principal Investigator (PI) has overall responsibility for the welfare of the trial subjects, design and conduct of the study, ensuring that IRB requirements and applicable regulatory requirements are met, and that the study site staff has knowledge of their responsibilities as required for their role in the study. It is the overall responsibility of the PI to ensure that all study data are complete and accurate and that all study records are placed in the study file.

The PI is responsible for the maintenance of the investigator file and IRB reporting, including writing the final report.

The PI or designee should maintain a list of appropriately qualified persons to whom significant study-related duties have been delegated and a signature sheet to document signatures and initials of all persons authorized to make entries or correction on study CRFs.

10.3 Dental Examiner

The Dental Examiner will be a qualified dental professional, such as a Dentist or Dental Hygienist. The Dental examiner will complete all dental examination activities, including dental photographs.

[figure not shown]
10.4 3M Staff Dentist

[REDACTED] Staff Dentist and will have clinical oversight for this study and complete all dental exam activities, including assessing adverse events.

10.5 Study Staff

The Study Coordinator(s) in the [REDACTED] Clinical Operations Division, are Laboratory/Technical Specialists who have extensive experience in all aspects of recruiting, screening, and consenting study subjects.

The Study Coordinator(s) assigned to this project will complete the recruitment of participants for this project, perform the screening procedures, the consenting process, and scheduling of all study-related visits/appointments. The Study Coordinator(s) will be

responsible for dispensing the study products assigned to each study subject, for providing and training subjects on subject diaries, and for completing CRFs that will be used at the assessment visits.

Study Coordinator(s) may be trained to assist the Dental Examiner during dental exams for activities that do not require a dental professional, such as uploading dental photographs, cleaning the exam room equipment, and scribing study CRFs.

Study Coordinator(s) will also share responsibilities with the Study Monitor in quality assurance procedures to ensure the integrity of the study data by assisting with checking the participants' responses on the study questionnaires, dental examination forms, study CRFs, and subject diaries for accuracy and legibility. The Study Coordinator(s) will assist in generating the final report for this project.

10.6 Study Monitor

The Study Monitor is responsible for ensuring the proper conduct of the study as regards protocol adherence and validity of the data recorded on the study CRFs. The Study Monitor will assist the PI and 3M in the maintenance of complete, legible, well-organized, and easily retrievable data. The Study Monitor will complete all monitoring activities in line with 3M Standard Operating Procedures (SOPs).

11.0 IRB

Using criteria set forth in Clinical Research Standard Operating Procedure ([REDACTED] Preclinical and Clinical Documentation Requirements), this study is considered to be the type of study requiring IRB approval before it can be conducted. Information concerning requirements for Investigational Review Board approval is addressed in Clinical Research Department Standard Operating Procedures ([REDACTED]).

12.0 Product Disposition

No special inventory is necessary because all materials remain in the control of 3M employees. All used and unused materials are to be returned to the Investigator.

13.0 Amendment / Deviations

13.1 Amendments

A protocol amendment is defined as a change in procedures that is identified and documented at any time while conducting the study. All protocol amendments must be documented and

approved by the Investigator, [REDACTED] Clinical Study Coordinator, and by the reviewing IRB prior to being implemented.

13.2 Deviations

A protocol deviation is defined as a change in procedure that has not been documented before initiation and therefore has not been reviewed and approved with the study sponsor prior to initiation. All deviations from the study protocol are to be documented and reported to the investigator and reviewing IRB.

14.0 Monitoring

Monitoring will be completed by the Study Monitor consistent with departmental SOPs and the study specific Monitoring Plan.

[figure not shown]

APPENDIX II – Randomization Schedule

Subject Number	Period 1	Period 2
01	B	C
02	A	C
03	C	B
04	B	C
05	C	B
06	A	C
07	C	B
08	A	C
09	B	C
10	B	C
11	A	C
12	C	B
13	C	B
14	A	C
15	C	B
16	B	C
17	A	C
18	B	C
19	A	C
20	A	C
21	B	C
22	C	B
23	B	C
24	C	B
25	A	C
26	C	B
27	A	C
28	C	B
29	B	C
30	B	C
31	A	C
32	C	B
33	B	C
34	B	C
35	A	C
36	C	B
37	A	C
38	A	C
39	B	C
40	C	B
41	C	B
42	B	C

Subject Number	Period 1	Period 2
43	B	C
44	A	C
45	B	C
46	A	C
47	C	B
48	C	B
49	C	B
50	A	C
51	B	C
52	B	C
53	A	C
54	C	B
55	B	C
56	C	B
57	A	C
58	B	C
59	A	C
60	C	B
61	C	B
62	A	C
63	B	C
64	B	C
65	C	B
66	A	C
67	A	C
68	B	C
69	C	B
70	C	B
71	B	C
72	A	C
